- a. **Informed Consent:** Informed consent for study participation will be obtained prior to subject participation commencement adhering to Kent IRB guidelines. Written informed consent will be the preferred method of consenting process. Should the participant not be able to provide written consent, verbal consent will be obtained and documented. Informed consent will be read aloud to key informants and ECHO participants and participants will be given time to ask questions before consenting to participate. The participants will be offered a copy of the informed consent documents to keep. For Aim 2, consent forms will be embedded within the electronic survey and participants will have the opportunity to ask questions about the study via email.
- b. **Protections Against Risk:** To minimize risks from potential disclosure of sensitive information, key informants and participants will have study procedures fully explained or described in writing before giving consent, with explanations about potential risks involved in participation. All participants will have ample time to ask questions prior to giving consent. No identifiable information will be collected during the interviews or surveys except names which will be kept in a linked codesheet and removed from the final database. All study materials will be stored either in a locked filing cabinet or electronically with two layers of security.

- c. The data safety monitoring plan will be designed by the principal investigator and mentors and will be submitted and reviewed in detail by the Care New England affiliated Institutional Review Board prior to any study procedures. Only the core study team will have access to survey data and transcribed interview data. The core study team includes the principal investigator ([name]), mentors ([name], [name] and [name]), and the medical student research assistant ([name]). No identifiable information will be collected during interviews or survey administration. We will code interviews and surveys with a unique identifier. Enrollment log linking unique IDs to participants (in the event that we need to contact them regarding interview or survey content) will be locked in a filing cabinet. Signed informed consent forms and any other study material will be stored in a separate locked filing cabinet.
- d. Qualitative data will be recorded using a digital voice recorder. Prior to interviews, demographic forms will be completed by each participant. These forms will be coded with a unique study ID. After each recording, the study team member will transfer all new recordings from the device to a password-protected computer in a locked office. The files will be labeled with the participants' unique study ID. The research assistant or the principal investigator will listen to the recording in the digital file and we will use NVivo to edit out any names or identifying information that may appear in the recordings, while incorporating unique IDs into the recordings so that participants can later be compared by characteristics. The original recordings with identifiable information will be deleted from the computer and the recording device after transcript cleaning takes place. Transcript files will be encrypted and stored securely in a password-protected file, on a password-protected computer and backed up on two password-protected external hard drives. Once analysis and research is completed, all recordings will be deleted from the computer and external hard drives.
- e. Quantitative data will be collected via REDCap or comparable survey program. Survey links will be shared with participants via email. At the time of informed consent, participants will provide their unique ID to the study team which will be stored on a separate page as listed above. The data from the surveys will be auto-populated into an electronic database. Only de-identified data will be entered into survey database. The database will be exported and saved on a password protected computer with at least two layers of protection. The database will be backed up on two password protected external hard drives after each of the eight survey periods. Hard drives will be stored in the locked filing cabinet with other study material.
- f. EMR data will be queried by the clinic sites' data team. We will provide them with the ECHO participant names and ask the team to code these names so that no provider names are identifiable to the study team at the time of database acquisition. BVCHC will be one of the clinic sites. The research team will acquire a de-identified database from the clinic, via the terms of the shared data agreement plan, with preliminary LTBI testing and treatment data. . The database will include provider names (not considered patient identifiers by BVCHC) which will allow linkage to ECHO provider participants. The database will be saved as a password protected file on password protected computers. The database will be backed up as explained above for the survey data.

Potential Benefits

Potential Benefits to Research Participants and Others: There will be no direct benefit to key informants. Participants who participate in the ECHO course will gain knowledge regarding TB infection testing and treatment that they may also pass on to colleagues and co-workers in their practices. If the ECHO course has a positive impact on learning and performance, this may ultimately increase the number of patients who are tested for TB infection and started on treatment. A successful ECHO course will also be an important component of an ECHO translational research framework at Brown and could be a model for future ECHO programs for other diseases in Rhode Island.

C. Risk-Benefit Ratio

Importance of the Knowledge to be Gained: This study will provide us with important information regarding the impact of the ECHO model on primary care team members' knowledge and performance regarding TB infection testing and treatment. The study will also provide, for the first time, important information about the knowledge, attitudinal, and skill gaps related to TB infection testing and treatment in primary care.

4) REFERENCES

Bibliography and References Cited

1. Jenkins HE. Global Burden of Childhood Tuberculosis. *Pneumonia* (Nathan Qld). 2016;8:24. doi: 10.1186/s41479-016-0018-6. PubMed PMID: PMC5166554.

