PROTOCOL

1.) TITLE OF PROJECT: Improving Rhode Island's tuberculosis preventive services in primary care: A mixed-methods evaluation of an innovative telementoring model

Principal Investigator (PI): [name], D.O., M.P.H.

Other Investigator(s): E. [name]., [name], [name], M.D., [name]

NCT 04188041

Last Update: 2/10/21

2.) Description of Study

A. Specific Aims

This pilot study will use a mixed-methods design called an exploratory sequential translational research design. In this type of study design, the initial qualitative phase informs the design of an intervention (in this case a TB infection ECHO) and an instrument (in this case structured surveys) to study an intervention. The final phase implements the designed intervention and/or instrument to collect data and quantitatively assess the outcomes of interest (in this case feasibility and impact).

Specific Aim 1: Explore the specific knowledge, attitudinal, and skills gaps to TB infection testing and treatment among primary care providers in RI through qualitative key informant interviews.

In Aim 1, at least 40 primary care team members from our Brown Family Medicine and Care New England networks will be purposively sampled to undergo key informant interviews regarding TB infection testing and treatment knowledge, attitudinal, and skill gaps. Questions will be asked to ascertain gaps throughout the entire latent TB infection care cascade. The results from Aim 1 will be used to design the survey instrument and the curriculum for an innovative, telementoring program (TB infection ECHO).

Specific Aim 2: Design and evaluate an evidence-based telementoring intervention (ECHO model) that addresses the identified TB infection gaps in Aim 1, and evaluate this model for feasibility as well as its impact on primary care team member knowledge and TB infection testing and treatment in RI.

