Aim 2: Survey Design: Quantitative pre- and post- ECHO course surveys and post-session surveys will be designed based on qualitative results from Aim 1 (Sample surveys have been uploaded in IRBnet and an amendment will be submitted with modified surveys after Aim 1 results are available). The PI will seek support from Advance-CTR faculty to build and manage surveys in REDcap or comparable survey program. These surveys will be used to assess the model's *feasibility* and *impact* on primary care team member knowledge and TB infection testing and treatment practices in RI. If it appears from Aim 1 results that there are several thematic segments in knowledge, attitudes, and skills, we will develop several questions related to each thematic segment. The surveys will include single-item binary and likert-type questions depending on the measure of interest. For example, questions related to learning as described below will be likert-type to improve reliability of our survey. The PI will ask mentors and Advance-CTR faculty to preliminarily review the surveys to ensure the questions are clear, concise, and not complex. The surveys will be pretested with five primary care volunteers.

To assess *feasibility*, we will explore process, resources, and management.³⁶ Feasibility data will be attained from iECHO, post-session evaluations, and post-ECHO course surveys. Process will include participant attendance, participant retention, case submission, and timing of the ECHO sessions. Resources will relate to connectivity issues and videoconferencing equipment availability at all sites. Management questions will relate to content expert facilitation and ease of communication with ECHO coordinator and content experts.

To assess *impact on providers*, we will use Moore's Expanded Outcomes Framework for Assessing Learners and Evaluating Instructional Activities²⁴ to study participants' self-reported learning and performance. Learning questions will focus on procedural knowledge (the degree to which participants state *how* to do what the activity intended them to know how to do). Procedural knowledge questions will focus on participants' self-reported confidence in latent TB infection testing and treatment. Performance questions will focus on the degree to which

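### Aim 2 promises impact on knowledge, but the only learning measure specified is self-reported confidence, so a pre/post change in the learning items would not show a change in knowledge

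*Combined protocol and SAP*

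**What the plan says.** Three places name knowledge as an outcome:

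- Section 2.A, Specific Aim 2, will evaluate the model's feasibility and "its impact on primary care team member knowledge and TB infection testing and treatment in RI".
- Section 2.E, Aim 2: Survey Design, says the surveys will assess feasibility and impact "on primary care team member knowledge and TB infection testing and treatment practices in RI".
- The Risk-Benefit Ratio section expects the study to give "important information regarding the impact of the ECHO model on primary care team members' knowledge and performance".

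The measure is set out in section 2.E. Impact on providers is studied as self-reported learning and performance. Learning means procedural knowledge, described as the degree to which participants state how "to do what the activity intended them to know how to do". The next sentence says how this is measured: "Procedural knowledge questions will focus on participants' self-reported confidence in latent TB infection testing and treatment". On format, "questions related to learning as described below will be likert-type to improve reliability of our survey".

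Section 2.G says that most impact questions are Likert-type. It compares the paired pre- and post-course responses by a Wilcoxon signed-rank test or a paired t-test, with significance at p < 0.05. It names no knowledge score.

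**The concern.** The outcome named and the outcome measured are different things. Confidence can rise after a course whether or not participants know more. With the learning measure as described, a rise in confidence with better knowledge cannot be told from a rise without it. Because the aim and the importance statement use the word knowledge, a significant change in these items could be read as a knowledge gain.

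This matters for the study's own rationale. Section 2.B justifies the project by the lack of evidence on the model's effect on primary care providers' knowledge, and section 2.C says the results will lay the foundation for a larger cohort study. A confidence result carried forward as knowledge would leave that gap open. A larger sample would not help, because the problem is what is measured and not how precisely.

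**Working it through.** **Step 1: is there a plan figure to reproduce?** No. Section 2.A says the sample size is limited by budget. It gives no effect size, SD, power or allowance for dropout. The main check is therefore a comparison of texts.

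**Step 2: definition against measure.** The definition in section 2.E requires participants to state how to do something, which can be judged right or wrong. The measure asks how confident they feel, and a Likert rating of confidence has no right answer. The two sit in consecutive sentences, so the mismatch is visible without any outside standard.

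**Step 3: does another component measure knowledge?**

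| Component | Where | What it captures |
|---|---|---|
| Learning items | 2.E | Self-reported confidence, Likert-type |
| Performance items | 2.E | Participants' own estimates of patients tested or treated |
| About 15 interviews | 2.A, 2.E | Practice change, course improvement |
| Post-session surveys | 2.A, 3.C | Said to assess impact as well as feasibility; items not described |
| Record review (Aim 3) | 2.E, 2.G | Tests ordered, treatment prescribed |
| Impact analysis | 2.G | Paired tests, mostly of Likert responses |

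No section describes a knowledge test, an answer key, a scored case or items marked correct or incorrect. Section 2.E does say that, if Aim 1 shows several themes in knowledge, attitudes and skills, "we will develop several questions related to each thematic segment", and it allows binary items. These depend on Aim 1 and their scoring is not stated. They do not amount to a specified knowledge outcome.

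**Step 4: what precision would a scored set have?** This does not size the defect. It only shows what a scored set could detect at the planned size.

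Inputs:
- Pairs: the course sample is at least 50 (2.A, 2.F, 3.C), at least 40 (2.E, Participant Recruitment) or 40 to 50 (3.A). The number of complete pre/post pairs is not stated, so 30 is an assumed lower case.
- Alpha 0.05 (2.G). Two-sided testing and 80% power are assumed.
- SD of the within-person change: 15 to 25 percentage points of items correct (assumed).

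For a paired t-test, find d such that a noncentral t variable with n − 1 degrees of freedom and noncentrality d√n exceeds the two-sided critical value with probability 0.80. The normal approximation (1.960 + 0.842)/√n gives a hand check. For n = 50 it is 2.802/7.071 = 0.396, slightly below the exact value, as expected.

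| Pairs | Detectable change (SD units) | SD 15 | SD 20 | SD 25 |
|---|---|---|---|---|
| 50 | 0.404 | 6.1 | 8.1 | 10.1 |
| 40 | 0.454 | 6.8 | 9.1 | 11.4 |
| 30 | 0.529 | 7.9 | 10.6 | 13.2 |

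The last three columns are percentage points: d multiplied by the SD, for example 0.404 × 15 = 6.1.

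**The case against.** The plan does not hide what it measures. Section 2.E says openly that learning is self-reported and names confidence, so knowledge in the aims can be read as a broad label that the methods then make specific. No sentence says a confidence change will be reported as a tested knowledge gain. The surveys filed with the IRB cannot be seen here. The learning questions are said to focus on confidence, which does not exclude other items. The outcomes framework that the plan cites might accept self-report at this level, and that cannot be checked from the documents. This is a budget-limited pilot whose impact evidence also includes interviews and record data that are not self-reported. A percent-correct test could itself measure recall and miss the plan's definition of stating how.

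Some of this stands. No concealment is alleged, scored items may exist, and the consequence depends on the final survey following the plan's description. The detectable changes rest on assumed SDs and say nothing about whether such a change is likely. The caution about item type is fair and affects the fix.

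The rest does not remove the point. Saying self-reported in one section does not reconcile it with three statements about knowledge. The interviews and the record review address practice and behaviour, not knowledge. The conflict between definition and measure lies in the plan's own text, whatever the cited framework allows.

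**Conclusion.** The concern holds for the plan as written. Knowledge is named as an outcome in three places, one learning measure is specified, and it is confidence. A significant change in the learning items would support a statement about reported confidence and nothing further. The performance items could separately support a statement about self-reported practice.

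No effect size is claimed for the gap, because the documents contain nothing that links confidence to knowledge. The conclusion concerns the plan, not the final survey. If the filed surveys contain scored items, the fault reduces to not naming that score as the outcome. The study can run as designed, but its learning conclusion should not be stated as knowledge without a correction.

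**What to change.** **Minimum.** In Specific Aim 2, the survey purpose in section 2.E and the Risk-Benefit Ratio section, call the learning outcome self-reported confidence, and limit the learning conclusion to it. This costs three wording edits and no new data, and can be done even if the surveys have already been fielded.

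**If the filed surveys already contain scored items.** Name that score as the knowledge outcome in section 2.G.

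**Better, if the pre-course survey has not been fielded.** Add a short scored set, identical before and after the course. Its items should ask participants to state how to carry out a step, so that they meet the definition in section 2.E and do not test recall alone. Name paired percent correct as the knowledge outcome in section 2.G, and report the Likert items separately as confidence. The planned paired tests apply unchanged, and the planned pretest can cover the new items ("The surveys will be pretested with five primary care volunteers").

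The costs are item writing and an answer key, content that suits roles from physicians to other team members (2.D), a few minutes in two of the eight surveys (3.C), and a possible retest effect from repeating items. Section 2.E plans a survey amendment after Aim 1, but section 3.C already refers to Aim 1 participation in the past tense, so the window may be closed. In that case no new items can be added and the relabelling is what remains.

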In Aim 2, at least 50 primary care team members will be recruited to participate in a virtual six-month TB infection ECHO course. Participants will complete quantitative surveys before and after the course as well as post-session surveys following each session. Survey questions will assess feasibility measures related to process, resources, and management and impact measures related to learning and performance. Paired data from pre- and post-course surveys will be analyzed accordingly depending on the distribution of results. The nature of this pilot project provides budgetary limits for an effective sample size. Therefore, for analyzed question responses that do not demonstrate a significant change between pre- and post- we will carefully note any relevant trends. In addition to the quantitative survey results, we will conduct approximately 15 qualitative interviews with ECHO participants. Given that practice change is difficult to assess quantitatively, questions will be asked regarding the impact of the ECHO course on practice change and about improvements that can be made to future LTBI ECHO courses.

Specific Aim 3: Pilot a retrospective electronic medical record (EMR) data review to examine RI PCPs' testing and treatment before and after ECHO implementation and evaluate the model's reach.

In Aim 3, data will be retrospectively extracted from two participants' clinics to research RI PCPs' testing and treatment patterns before and after the ECHO course. Aim 3 will evaluate the model's reach, or the degree to which the population that is eligible to benefit from an intervention actually benefits. In the case of LTBI, there is one lab test type (interferon gamma release assay) and two medications (rifampin and isoniazid) used. They are used sparingly for other ailments in primary care. Therefore, LTBI lab tests and prescriptions could be an excellent proxy measure of providers' behavior change related to LTBI testing and treatment, and ultimately the reach of the ECHO model.

B. Background

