Potential variables related to testing and treatment will be discussed with the health centers or clinic sites, and data extraction will be requested through the site's data team. Data variables to be queried will include provider ECHO enrollment, HIPAA compliant patient demographic information, ICD-10 diagnosis code to separate TB disease from TB infection, TB infection laboratory testing data, and LTBI prescriptions. At Blackstone Valley Community Health Center, the following additional information will be included in the database: age, gender, primary language, country of origin, refugee status if available, ICD-10 diagnoses to separate TB disease from TB infection, date of IGRA test, type of IGRA test, IGRA test result, LTBI evaluation including chest x-ray and documentation of symptom screen, LTBI treatment plan including referral and/or LTBI treatment initiation (medications such as rifampin or isoniazid), and treatment completion or documentation from specialist of LTBI treatment completion. Data will be retrospectively collected to capture the three months prior to LTBI ECHO implementation, six months during the LTBI ECHO, and three months after LTBI ECHO implementation. We will work with health center sites to determine the best way to link ECHO participants to health center data. This could include health centers including provider names in the database if acceptable or providing health centers with names of their ECHO provider participants and having them code the database in a way that enables the study team to differentiate ECHO participants from other providers and protect anonymity. [name] in her role as co-investigator will oversee the ECHO participant linkage with health center data.

G Data Analysis

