For the impact analysis, the majority of these questions will be likert-scale type. The distributional properties of the pre- and post- responses will be examined. The paired data will be analyzed using Wilcoxon-signed rank test or a paired t-test depending on whether or not the responses seem to be following a normal distribution. Significance will be considered if *p-value* is < 0.05 .

Regarding Aim 3, Blackstone Valley Community Health Center has been selected as one of our sites. Currently, BVCHC staff are reviewing patient charts for clinical purposes in order to design a latent TB infection clinic. Therefore, a de-identified database with LTBI tests ordered and LTBI prescriptions written by PCPs exists. For the purpose of this study and after written approval from BVCHC, this de-identified patient database will be provided to the study team as per the data sharing agreement. Once we identify another site, data variables from the two EMRs will be sorted, matched, and coded synchronously so that all data can be analyzed together. We will work with health center sites to determine the best way to link ECHO participants to health center data. Descriptive statistics will be performed to determine the number of LTBI tests ordered and LTBI treatment prescribed by PCPs in each time period (before, during, after). We will study potential denominators including total number of patient visits, number of wellness visits, number of patients diagnosed with LTBI, and number of visits with immigrant/refugee patients to explore the best potential measures of effectiveness in future studies. Comparison between the ECHO participants and non- ECHO participants will also be considered to assess initial trends.

H. Material Inducements

Knowledge gained.

I. Training of Research Personnel

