The retrospective chart review will involve data from ECHO participants as well as data from other providers who have ordered a TB test or prescribed LTBI medication at the two health care centers or clinics that are selected.

B. Recruitment and Consent Procedures

Specific Aim 1: In this aim, at least 40 key informant interviews with primary care team members in Rhode Island will be performed. The department of Family Medicine has a list of all primary care providers who are alumni or are community preceptors. There is also a list of primary care providers including other specialties like internal medicine and pediatrics throughout Care New England. Using these contact lists, participants will be recruited via email initially. Several chief medical officers at federally qualified health centers have given us permission to also circulate recruitment emails via health center listserves to recruit their primary care team members. For those who do not respond positively or negatively, a phone call to their primary care office during business hours will be made. If the participant agrees to be interviewed, a convenient time will be arranged to meet with the participant. Interviews will be performed in a quiet, private location either at the participant's office or in the department of Family Medicine at [name]. Given primary care team members' busy schedules, interviews may also be conducted via phone. In this case, informed consent documents will be sent via the participant's preferred method, email or mail. The consent will be read aloud over the phone, and the verbal consent will be documented by the study team by signing the informed consent and writing a note that informed consent was obtained over the phone for the participant. We will attempt to reschedule interviews up to three times for participants in order to retain them in the interview process.

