(Zoom) every month for six months. Participants will receive continuing medical education credit if they attend 4/6 sessions. Clinical cases presented during ECHO sessions will be de-identified and no identifiable information will be shared with participants. All quantitative surveys will be designed and administered via Qualtrics. Each participant will be asked to complete eight surveys: one pre-course, six post-session, and one post-course. Demographic information (same as in Aim 1) will be collected on the pre-course survey. Potential Risks – There is a small risk of disclosure of sensitive information during the TB infection ECHO course by participants. *Minimization:* To reduce this risk, standard ECHO procedures will be followed and clinical cases will be reviewed by the ECHO coordinator, content expert, and/or principal investigator prior to the session to ensure no identifiable information is included.

Aim 3: Study procedures and materials – For the retrospective EMR data query, two clinic sites will be chosen. In order to explore this EMR data query, we are acquiring a de-identified database from BVCHC, obtained via the terms of the data agreement plan, in order to assess preliminary LTBI testing and treatment. We had several BVCHC staff participate in Aim 1 so we are hopeful that this site will include participants from the ECHO course who attended at least 4/6 sessions. The database will include provider names (not considered patient identifiers by BVCHC) which will allow linkage to ECHO provider participants. The data query will involve the variables listed in part 2 section F: Specific Procedures or Treatments. Additional de-identified variables may be added in consultation with the two clinic sites if they are important variables to consider that may impact LTBI testing and treatment. Potential Risks – There is a small risk of disclosure of PHI during the data query process. We will work closely with the clinic sites' data teams to ensure that no PHI is provided to our team during this process and will follow the procedures as stated in the data sharing agreement. The database will be kept in a password protected file on password protected computers, and only the study team will have access to it.

D. Protection of the Subject

1. Adequacy of Protection Against Risks

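### The Aim 3 extract contains each calendar month once, so counts before and after the course cannot be separated from season or drift

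*Combined protocol and SAP*

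**What the plan says.** Section 2.A describes Aim 3 as follows: "Pilot a retrospective electronic medical record (EMR) data review to examine RI PCPs' testing and treatment before and after ECHO implementation". It adds that "LTBI lab tests and prescriptions could be an excellent proxy measure of providers' behavior change related to LTBI testing and treatment". Section 2.F sets the extract to "capture the three months prior to LTBI ECHO implementation, six months during the LTBI ECHO, and three months after LTBI ECHO implementation". Section 3.C says that the course sessions run "every month for six months".

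The Aim 3 analysis in Section 2.G is descriptive: "the number of LTBI tests ordered and LTBI treatment prescribed by PCPs in each time period". Several denominators will be explored, including total visits, wellness visits and visits with immigrant or refugee patients. No calendar matching, trend term or seasonal adjustment is mentioned. On a concurrent control, Section 2.G says: "Comparison between the ECHO participants and non- ECHO participants will also be considered to assess initial trends". Section 3.A describes the non-ECHO records as "data from other providers who have ordered a TB test or prescribed LTBI medication at the two health care centers".

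**The concern.** The only baseline is one quarter of the year, and the follow-up is a different quarter. Anything that makes LTBI testing or prescribing vary by time of year, or rise or fall steadily, enters the before/after difference together with any effect of the course.

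The documents name one possible source of drift. The health center already chosen as a site (BVCHC) is reviewing charts in order to design an LTBI clinic, which could change testing there whether or not its staff attend ECHO.

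What is at stake is the reading of the counts as a sign of changed provider behavior and of reach, and the choice of effectiveness measures for later studies. It is hard to judge a measure whose ordinary month-to-month variation has not been observed.

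**Working it through.** The documents give no rate, effect size, sample size or power for Aim 3, so there is no stated figure to reproduce. The window lengths come from Section 2.F and the course length from Section 3.C. The seasonal amplitudes and drift rates below are assumptions, shown as ranges.

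**1. Windows.** Put the course start at month 0. Before runs from −3 to 0, during from 0 to 6, and after from 6 to 9. The midpoints are −1.5 and 7.5, so the separation is 7.5 − (−1.5) = 9 months. The total is 3 + 6 + 3 = 12 months. Each calendar month occurs once, and before and after share none.

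**2. Can the after effect be estimated from ECHO providers alone?** Twelve monthly values and twelve calendar-month terms leave nothing with which to estimate a course effect. If season is assumed to be one smooth annual cycle, the effect can be estimated, but only through that assumed shape. Its variance is then 1.14 times the monthly residual variance, or 5.10 with linear drift added, against 0.67 with neither. Section 2.G plans no such model, and three period totals could not support one.

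**3. Size of a seasonal artefact.** For a sinusoidal season of amplitude A (as a fraction of the mean), averaging over 3 months keeps sin(π/4)/(π/4) = 0.900 of the swing. At 9 months' separation:

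- Maximum difference = 2A × 0.900 × sin(9π/12) = 2A × 0.900 × 0.707 = 1.27A. For A = 10%, 20% or 30% this is 13%, 25% or 38% of the mean.
- Average absolute difference over all start months = 1.27A × 2/π = 0.81A, which is 8%, 16% or 24%.
- As after/before ratios, the extremes are 0.88 to 1.14, 0.77 to 1.30 and 0.67 to 1.48. The error can go either way.

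**4. Size of a drift artefact.** For growth g per month, the spurious ratio over 9 months is (1 + g)^9: 1.09 at 1% and 1.20 at 2%.

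**5. What a longer baseline buys.** The table gives the variance of the after effect, in units of the monthly residual variance, in a model with a term for each calendar month. The last column assumes that non-ECHO providers share the season and the drift.

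| Months before the course | ECHO alone, no drift | ECHO alone, linear drift | ECHO and non-ECHO, linear drift |
|---|---|---|---|
| 3 (planned) | not estimable | not estimable | 1.33 |
| 6 | 0.67 | not estimable | 1.00 |
| 12 | 0.67 | not estimable | 0.69 |
| 13 | 0.67 | 2.67 | 0.64 |
| 24 | 0.50 | 0.88 | 0.51 |

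Months −6 to −3 are the after quarter one year earlier, and months −12 to −6 match the during window. With 12 months no calendar month repeats within the baseline, so drift still cannot be separated from the course effect in the ECHO series alone.

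**6. Precision.** At a constant monthly rate, pooling 12 baseline months in place of 3 changes the standard error of the log after/before rate ratio by a factor of √[(1/12 + 1/3)/(1/3 + 1/3)] = √0.625 = 0.79, a 21% reduction. A calendar-matched contrast sets 3 months against 3 and gains nothing.

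**The case against.** The strongest answer is the concurrent comparison. Non-ECHO colleagues at the same sites share season and site-wide drift, and step 5 shows that the after effect is then estimable even with the planned three-month baseline. This stands in principle, but the plan only says that the comparison will be considered and gives no method. The comparators are also selected on the outcome: a provider enters by having ordered a test or prescribed, so those who did neither are missing. Participants choose to enrol, and the Potential Benefits section expects them to pass knowledge to co-workers. The comparison would reduce the problem without removing it.

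Second, a reader might infer that seasonality in wellness or immigrant/refugee visits would itself appear as an ECHO effect. The plan lists those visits as candidate denominators, and dividing by them cancels proportional swings in that visit volume. What remains is seasonality in raw counts, in rates over another denominator, or in testing per visit.

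Third, a reader might infer that a planned inference is invalid. Aim 3 has no test, threshold or effect claim, and the 0.05 level in Section 2.G belongs to the survey analysis.

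Fourth, it is tempting to say that a longer baseline is there for the asking. The documents confirm only that prescription data can be queried in the record system at the Family Care Center, which is not named as an Aim 3 site. The BVCHC database comes from staff chart review with no stated date span, and the second site is not yet identified.

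**Conclusion.** The point holds as a limit on interpretation, and dealing with it looks cheap. With the 3/6/3-month extract and counts by period, a change in ECHO providers' testing or prescribing cannot be separated from season or drift. If the seasonal amplitude were 10% to 30% of the mean, the artefact could reach 13% to 38% and would average about 8% to 24%, less with a denominator that shares the season. These sizes rest on an assumed sinusoid, because the documents give no amplitude.

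Two stronger readings of the remedy are not supported. Comparing with the same months a year earlier deals with season but not with drift: it lengthens the separation from 9 to 12 months, so the drift ratio rises from 1.09 to 1.13 at an assumed 1% per month and from 1.20 to 1.27 at 2%. The 21% precision gain holds only if the 12 baseline months are pooled, and should not be claimed for the calendar-matched contrast.

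**What to change.** - Ask each site how far back its records go. Start the extract at least 12 months before the course, and 24 months where available, since 12 cannot separate season from drift in the ECHO series alone.
- Report monthly counts and rates. Show both the calendar-matched contrast and the immediate before/after contrast, because the first is more exposed to drift and the second to season.
- Commit to the ECHO versus non-ECHO comparison. Define the comparators as all PCPs at the site, whether or not they ordered a test or prescribed.
- If earlier data cannot be obtained, state that before/after differences cannot be attributed to the course.

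The cost is more months of records for the sites' data teams and possibly an IRB or data-agreement amendment. If the BVCHC records have to be abstracted by hand, the extension there could be limited to test and prescription dates.
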